3.0 Endpoints

The following endpoint definitions apply to the efficacy variables described below:

- **Clinical remission per PROs:** average daily very soft or liquid SF ≤ 2.8 AND average daily AP score ≤ 1.0 and both not greater than baseline
- **Clinical remission per CDAI:** CDAI < 150
- **Enhanced Clinical Response:** $\geq 60\%$ decrease in average daily very soft or liquid SF and/or $\geq 35\%$ decrease in average daily AP score and both not greater than baseline, or clinical remission per PROs
- **Clinical response 100 (CR-100):** decrease of at least 100 points in CDAI from Baseline
- **Clinical response per PROs:** $\geq 30\%$ decrease in average daily very soft or liquid SF and/or $\geq 30\%$ decrease in average daily AP score and both not greater than Baseline
- **Endoscopic remission:** SES-CD ≤ 4 and at least 2 point reduction from Baseline and no subscore > 1 in any individual variable, as scored by central reviewer

- **Endoscopic response:** decrease in SES-CD > 50% from Baseline of the induction study (or for subjects with an SES-CD of 4 at Baseline of the induction study, at least a 2 point reduction from Baseline), as scored by central reviewer

Details of CDAI, SES-CD and PRO questionnaires are provided in [Appendix D](#), [Appendix E](#) and [Appendix F](#) respectively.

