 - Markov Chain Monte Carlo (MCMC) will be first applied to augment data into monotonic missing pattern (where applicable) and PROC MI will be used to generate 30 datasets using the regression method. If the binary endpoints are derived from the continuous variables, PROC MI will be applied to the continuous variables. The variables to be included in the imputation model are: treatment group, randomization stratification factors (baseline steroid use (Yes, No), endoscopic disease severity (SES-CD < 15, ≥ 15) and number of prior biologics with inadequate response or intolerance (≤1, > 1)), age, gender, weight, baseline measurement (if applicable) and post-baseline measurements at each visit up to the end of the analysis period. The random seed for MCMC and the random seed for PROC MI are specified in [Appendix I](#). The imputed post-baseline measurements will be rounded to the same precision as the observed data before the determination of responder status. Subjects will be characterized as responders or non-responders based on MI imputed data. Using the CMH model adjusted by randomization stratification factors, the endpoints will be analyzed using each of the 30 imputed datasets. SAS PROC MIANALYZE will be used to generate the final inferences of the risk difference between upadacitinib group and placebo group, using Rubin's rule³. Note that measurements will be set to missing for 1) at or after the occurrence of the CD-related corticosteroids intercurrent event 2) on/after the date of initiation of CD-related confounding medications after premature discontinuation of study drug

before applying MI. After the MI imputation, an NRI override will be implemented for missing values 1) missing values due to reasons other than COVID-19 infection or logistic reasons, or 2) at or after the occurrence of the CD-related corticosteroids intercurrent event or 3) on/after the date of initiation of CD-related confounding medications after premature discontinuation of study drug, that is, regardless of MI imputed values, subjects satisfying 1) or 2) or 3) will be considered as "non-responder" for binary efficacy endpoints.

For binary efficacy endpoints regarding the occurrence of hospitalization and the occurrence of CD-related surgeries, missing data will be handled using the following approaches.

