The tipping point analyses are two-dimensional, i.e., assumptions about the missing outcomes on each of the upadacitinib group and the placebo group can vary independently. In addition, the focus is on scenarios where missing outcomes on upadacitinib are worse than the imputed values on upadacitinib, while missing outcomes on placebo are better than the imputed values on placebo. Missing values are first imputed via MI under MAR assumption, and then a shift parameter is applied to the imputed values (a different shift parameter may be specified for each treatment group). This is implemented by PROC MI using the MNAR statement. The imputation uses a two-step approach, augmentation step using MCMC and imputation step using Monotone Regression. The MNAR statement is applied in the imputation step. The number of imputed datasets is 30.

In cases where the shifted values are smaller than the minimum or larger than the maximum value of the endpoint, (i.e., out of range), the minimum or maximum value of the endpoint is used in further analysis steps. For each pair of shift parameters, the same MMRM/ANCOVA method used for the primary analysis will be performed on each of the imputed datasets to obtain the results for each upadacitinib treatment group versus the placebo group comparison.

These results will be aggregated using Rubin's rule.³

- If a pair of shift parameters is found to reverse the study result interpretation in terms of p-value larger than 0.05, then the pair of shift parameters is identified as the tipping point.

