Appendix E. Simple Endoscopic Score – CD (SES-CD)

SES-CD is calculated based the sum of individual segment values for four endoscopic variables (presence and size of ulcers, ulcerated surface, affected surface and presence of narrowing). Each variable in each segment be scored 0 to 3 resulting in SES-CD values ranging from 0 to 56 with higher scores indicating more severe disease.

Variable	Score			
	0	1	2	3
Size of ulcers (cm)	None	Aphthous ulcers (diameter 0.1–0.5)	Large ulcers (diameter 0.5–2)	Very large ulcers (diameter >2)
Ulcerated surface (%)	None	<10	10–30	>30
Affected surface (%)	Unaffected segment	<50	50–75	>75
Presence of narrowings	None	Single, can be passed	Multiple, can be passed	Cannot be passed

* Total SES-CD: sum of the values of the 4 variables for the 5 bowel segments. Values are given to each variable and for every examined bowel segment (for example, rectum, left colon, transverse colon, right colon and ileum).

Medscape Source: Nat Rev Gastroenterol Hepatol ©2009 Nature Publishing Group

[figure not shown]
SES-CD Scoring:

	Rectum	Sigmoid and Left Colon	Transverse Colon	Right Colon	Ileum	Total
Size of Ulcers Enter: 0 if none 1 if aphthous ulcers (Ø 0.1 to 0.5 cm) 2 if large ulcers (Ø 0.5 to 2 cm) 3 if very large ulcers (Ø > 2 cm)						
Ulcerated Surface Enter: 0 if none 1 if < 10% 2 if 10% – 30% 3 if > 30%						
Affected Surface Enter: 0 if unaffected segments 1 if < 50% 2 if 50% – 75% 3 if > 75%						
Presence of Narrowing Enter: 0 if none 1 if single, can be passed 2 if multiple, can be passed 3 if cannot be passed						
					TOTAL =	

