Appendix I. Random Seeds

In case of non-convergence, the random seed will be updated by adding 100000 at each attempt until convergence of model happens.

Table I-1. Random Seeds for NRI-C

Variables	Random Seed	
	MCMC Procedure	PROC MI
CDAI	14431	24431
SES-CD (for 20 individual variables)	N/A	24432
SF	14441	24441
AP score	14451	24451
EIM	N/A	24452
IBDQ total score	14461	24461
FACIT-F	14471	24471
CGHAS	14491	24491

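### Linear regression with rounding on the 20 SES-CD items (each 0 to 3) under-imputes endoscopic remission; imputing the yes/no endpoint directly is a cheap improvement

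*SAP*

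**What the plan says.** NRI-C is the main analysis for the co-primary endpoints (SAP 9.3.2) and for the categorical ranked secondaries other than CD hospitalization (SAP 9.4.1). Missing data count as non-response unless the cause is COVID-19, in which case multiple imputation is used.

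SAP 9.2.1 describes that imputation:
- The method: "PROC MI will be used to generate 30 datasets using the regression method".
- Its target: where a yes/no endpoint is built from an underlying continuous score, the imputation acts on that score and not on the endpoint.
- Its treatment of imputed values: "The imputed post-baseline measurements will be rounded to the same precision as the observed data before the determination of responder status".

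The row for the endoscopic score in SAP Appendix I, Table I-1, begins "SES-CD (for 20 individual variables" and has a PROC MI seed but no MCMC seed. SAP Appendix E gives the scale of these items: "Each variable in each segment be scored 0 to 3".

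Two endpoints depend on the imputed items (SAP 3.0). Endoscopic response needs a "decrease in SES-CD > 50% from Baseline of the induction study", with a 2-point rule for a baseline score of 4. Endoscopic remission needs a total of at most 4, a reduction of at least 2 points, and "no subscore > 1 in any individual variable, as scored by central reviewer".

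The SAP handles out-of-range values in one place, the tipping-point analysis for continuous endpoints (SAP 9.2.3), where "the minimum or maximum value of the endpoint is used in further analysis steps". NRI-C has no such rule. It also does not give the order of the 20 items, or say whether each is regressed on all 20 baseline items, on its own baseline only, or on the other Week 12 items.

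**The concern.** The items are short ordinal scores, likely with many zeros. The regression method draws each from a normal distribution with one residual variance, and rounding to integers does not prevent a value of -1. Two things follow.

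- **Remission.** A single item above 1 defeats it. Independent noise across 20 items makes that likely even in a subject whose mucosa would have healed.
- **Response.** It depends on the total. Negative items cancel positive ones and lower the total; truncating them at zero raises it. The net error therefore depends on how the items are modelled.

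At stake is the imputed part of one co-primary and one ranked secondary, in the analysis that supplies the headline estimates. SAP 9.2 states that the aim is a reliable estimate of the effect as it would be without the pandemic.

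**Working it through.** **1. The plan's own figure.** SAP 2.4 assumes endoscopic response of 10% on placebo and 25% on upadacitinib, with 165 and 330 subjects, Fisher's exact test and two-sided 0.05, and claims at least 95% power. Exact enumeration gives 98.65%, so the claim is met. The documents give no figure for imputation error.

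**2. Simulation set-up.** From the documents: 330:165 allocation, 5 segments by 4 items scored 0 to 3, linear regression, 30 imputations, rounding, and the predictors in SAP 9.2.1. Assumed: the item distributions (three scenarios with about 10% placebo response and 23% to 47% upadacitinib response) and 10% of Week 12 endoscopies missing at random. There were 130 simulated trials per scenario. Three readings were tried: joint with all 20 baseline items; joint with the item's own baseline; each item separately with its own baseline. Under the first reading, about 7% to 9% of imputed item values fell below 0 and at most 0.3% above 3.

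**3. Results among imputed subjects, no truncation.**

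| | Bimodal | Unimodal | Larger effect |
|---|---|---|---|
| Upadacitinib remission, true | 17.7% | 11.7% | 32.5% |
| joint, all baselines | 7.5% | 7.1% | 17.4% |
| joint, own baseline | 6.6% | 6.3% | 17.2% |
| separate | 1.9% | 2.3% | 7.8% |
| Placebo response, true | 10.2% | 9.4% | 10.2% |
| joint, all baselines | 17.0% | 12.5% | 16.5% |
| joint, own baseline | 11.8% | 7.8% | 11.8% |
| separate | 2.5% | 1.3% | 1.7% |
| Upadacitinib response, true | 22.7% | 22.7% | 46.1% |
| joint, all baselines | 26.6% | 26.0% | 46.0% |
| joint, own baseline | 22.7% | 22.0% | 46.0% |
| separate | 9.9% | 10.8% | 41.8% |

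The relative shortfall in upadacitinib remission is 1 - imputed/true. It is 39% to 63% for the joint readings (for example 1 - 7.1/11.7 = 39%) and 76% to 89% for the separate reading. Other simulations with different assumed distributions gave 29.4% true against 16.5%, 20.1% against 9.8%, 30.1% against 15.0%, and 24.7% against 16.3%: shortfalls of 34% to 51%.

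**4. Truncation to 0 to 3 (joint, all baselines).** Upadacitinib response falls to 11% to 29% (true 23% to 46%), and upadacitinib remission to 4.4% to 11.6% (true 12% to 33%). Both are worse than without truncation.

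**5. Effect on the trial.** Shift in the treatment difference = missing share × (imputed difference - true difference).
- Remission, joint with all baselines, bimodal: imputed 7.5 - 4.6 = 2.9, true 17.7 - 8.5 = 9.2, so -6.3 points among imputed subjects. At 2% missing this is -0.13 points; at 10%, -0.63.
- Remission, both joint readings, all scenarios: -0.07 to -1.2 points over 2% to 10% missing. The separate reading reaches -1.7 in the larger-effect scenario at 10%.
- Response, separate: -5.1 points among imputed subjects in the bimodal scenario, but +4.2 in the larger-effect scenario (41.8 - 1.7 = 40.1 against 46.1 - 10.2 = 35.9). The sign is not fixed.

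**6. Power for endoscopic response.** Overall rate = (1 - f) × design rate + f × imputed rate, using imputed rates of 17% and 28% (joint, all baselines, bimodal; 28% is rounded up).
- f = 5%: 10.35% vs 25.15%, difference 14.8 points, Fisher power 98.3%.
- f = 10%: 10.7% vs 25.3%, difference 14.6 points, power 97.9%.
- Separate reading (2% and 10%), f = 10%: 9.2% vs 23.5%, difference 14.3 points, power 98.35%.

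**The case against.** **The model may not be linear.** In Table I-1 only the SES-CD items and extra-intestinal manifestations lack an MCMC seed, and both are categorical, so a categorical model might be intended. This is possible, but SAP 9.2.1 names no other method. If one is meant, the text still needs to say so.

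**The range rule in SAP 9.2.3 is not a true contrast.** It covers values moved by the tipping-point shift parameter. This stands: the absence of a rule in NRI-C is silence rather than contradiction.

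**Planned analyses already cover the risk.** NRI-NC uses no imputation model, and the binary tipping point assigns yes/no status directly over 0% to 100% in each arm (SAP 9.2.3, 9.3.3, 9.4.2). They limit the consequences, but they do not correct the primary estimate.

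**A stronger reading is tempting:** that the method makes placebo responders too frequent whatever the predictors, and so pulls the co-primary toward no difference. The documents do not support it. Placebo response is clearly too high only in joint, untruncated models using all baseline items. It is near truth with the own-baseline predictor, which fits the singular wording for the baseline measurement in SAP 9.2.1 at least as well, and far too low when items are imputed separately. The SAP does not settle which applies.

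**Conclusion.** A cheap improvement, not a threat to the trial. The stated method does not suit 0-to-3 items, and it under-imputes endoscopic remission on upadacitinib under every reading tried. For endoscopic response, joint untruncated models give placebo rates from near truth to too high, while separate or truncated models give response that is too low, clearly so on upadacitinib in most scenarios.

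Over an assumed 2% to 10% COVID-missing share, the remission or response difference moves by roughly 0.1 to 1 point, somewhat more only in the most adverse combination, and power for the co-primary stays near 98%. A reader might infer that the co-primary conclusion is at risk; these figures do not support that.

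The percentages are illustrative, because the item distributions, the missing share and missingness at random are assumptions. The direction for upadacitinib remission is consistent across them; the direction for response is not.

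**What to change.** In SAP 9.2.1 and Table I-1, for endoscopic response and endoscopic remission, impute the yes/no endpoint directly by logistic regression (PROC MI, MONOTONE LOGISTIC) with treatment, the stratification factors and baseline SES-CD as predictors. Keep the existing non-responder override.

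In simulation this stayed close to truth:
- Response (upadacitinib vs placebo): 32.5% vs 11.1% (true 33.2% vs 10.2%) and 34.6% vs 12.4% (true 33.7% vs 11.3%). The largest miss elsewhere was 23.1% against 26.6% true on upadacitinib.
- Upadacitinib remission: 29.2% (true 30.1%) and 26.6% (true 24.7%).

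Do not rely on truncating the items to 0 to 3, or on predictive mean matching of the items, which did not remove the error either.

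The cost is a wording change and new seed rows. There are two downsides. Response and remission are imputed separately, so an imputed subject could have an inconsistent status. The other item-based endpoints in SAP 3.3.1, such as SES-CD of at most 2 and the ulcerated-surface endpoints, need their own stated imputation.

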#### **Diary Based**

The ePRO data (number of total and liquid or very soft stools, stool consistency per Bristol Stool Chart, use of medications used for endoscopy preparation, if an endoscopy was performed, AP, and general well-being) will be collected electronically via a handheld device into which the subject will record the required pieces of information on a daily basis. The electronic device will be programmed to allow data entry once per day.

All data entered on the device will be immediately stored to the device itself and manually/automatically uploaded to a central server administrated by CRF Health. The investigational site staff will be able to access all uploaded subject entered data via a password protected website, up until the generation, receipt and confirmation of the study archive.

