2.4 Sample Size Determination

The co-primary endpoints are achievement of clinical remission per PROs (EU/EMA) or per CDAI (US/FDA) at Week 12 and achievement of endoscopic response at Week 12. Sample size calculation is based on the maximum sample size needed to detect treatment difference for each of the co-primary endpoints. The proposed assumptions were informed by the results of the 16-week clinical and endoscopic data of upadacitinib Phase 2 CD Study M13-740.

For EU/EMA regulatory purposes: Assuming a rate of 12% for clinical remission per PROs in the placebo group and 29% in the upadacitinib group at Week 12, a total sample size of 495 subjects randomized in a 2:1 ratio (330 subjects in the upadacitinib group and 165 subjects in the placebo group) will be adequate to detect at least a 17% treatment difference in clinical remission per PROs rates at Week 12 between the treatment groups using Fisher's exact test with at least 95% power at a 0.05 two-sided significant level.

For US/FDA regulatory purposes: Assuming a rate of 20% for clinical remission per CDAI in the placebo group and 40% in the upadacitinib group at Week 12, the same

sample size of 495 subjects will be adequate to detect at least a 20% treatment difference in clinical remission per CDAI rates at Week 12 between the treatment groups using Fisher's exact test with at least 95% power at a 0.05 two-sided significant level.

Assuming an endoscopic response rate of 10% in the placebo group and 25% in the upadacitinib group at Week 12, this sample size will be adequate to detect at least a 15% treatment difference in endoscopic response rates at Week 12 between the treatment groups using Fisher's exact test with at least 95% power at a 0.05 two-sided significant level.

In Part 2, assuming a Week 12 clinical response rate of approximately 52% among the subjects treated with upadacitinib 45 mg QD, an additional 150 subjects enrolled in Part 2 would provide adequate number of subjects achieving clinical response to be re-randomized to the maintenance portion of Study M14-430.

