9.2.1 Categorical Endpoints

For binary efficacy endpoints other than the occurrence of hospitalization and the occurrence of CD-related surgery, missing data will be handled using the following approaches:

- The primary approach for handling missing data in the analysis of binary endpoints will use **Non-Responder Imputation (NRI)** while incorporating Multiple Imputation (MI) to handle missing data due to **COVID-19 (NRI-C)**.
 - The NRI-C will categorize any subject who does not have an evaluation during a pre-specified visit window (either due to missing assessment or due to early withdrawal from the study) as a non-responder for the visit. The only exception is that missing data due to COVID-19 infection or logistical restriction will be handled by MI. At each visit, subjects will be characterized as responders or non-responders based on MI imputed values if missing due to COVID-19; otherwise, subjects will be considered as non-responders for missing due to other reasons in the NRI-C approach. In addition, at and after the CD-related corticosteroids intercurrent event (see Section 8.2) and on/after the date of initiation of CD-related confounding medications after premature discontinuation of study drug (see Section 8.1), subjects will be considered as non-responders and will not be imputed by MI.

- A sensitivity analysis for binary endpoints will use **NRI** with **No** special data handling for missing due to **COVID-19** (NRI-NC).
 - NRI-NC will be performed in the same way as NRI-C without the exception above. Missing due to COVID-19 infection or logistical restriction will also be counted as non-responders. Subjects on or after the occurrence of the CD-related corticosteroids intercurrent event and on/after the date of initiation of CD-related confounding medications after premature discontinuation of study drug will still be considered as non-responders. This is the same method as "NRI" as defined in the protocol.
- Details on MI method in NRI-C are described below:

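### The SAP appears to impute stool frequency and abdominal pain separately although PRO remission needs both; if the two are positively correlated, imputed remission is slightly too low, and a joint model avoids this at almost no cost.

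*SAP*

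**What the plan says.** - **Endpoint.** SAP 3.0 defines clinical remission per PROs as "average daily very soft or liquid SF ≤ 2.8 AND average daily AP score ≤ 1.0 and both not greater than baseline". Both symptoms must qualify in the same subject.
- **Who is imputed.** NRI-C is the main missing-data method for the co-primary endpoints (SAP 9.3.2). Missing values count as non-response, and SAP 9.2.1 adds: "The only exception is that missing data due to COVID-19 infection or logistical restriction will be handled by MI". Values after the specified intercurrent events also count as non-response.
- **What is imputed.** SAP 9.2.1: "If the binary endpoints are derived from the continuous variables, PROC MI will be applied to the continuous variables". Responder status is derived afterwards.
- **Predictors.** SAP 9.2.1 lists treatment, the stratification factors, age, gender, weight, and "baseline measurement (if applicable) and post-baseline measurements at each visit up to the end of the analysis period". It does not say whether the SF model contains AP or the AP model contains SF.
- **Seeds.** In Appendix I, "Table I-1. Random Seeds for NRI-C", SF has its own row (MCMC 14441, PROC MI 24441) and so does AP (14451, 24451). By contrast, one row and one PROC MI seed (24432) cover "SES-CD (for 20 individual variables").

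**The concern.** Where the SAP handles several variables together, as for the SES-CD items, Table I-1 gives them one row. SF and AP have two rows, and the predictor list does not link them. The natural reading is two separate imputation runs.

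In that case the imputed SF and AP values for a subject are independent of each other given the predictors. Any residual correlation between them is lost before the both-must-qualify rule is applied. With positive residual correlation, the chance that both are low is larger than the product of the separate chances, so imputed remission is too low.

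The estimate concerned is the main analysis of an EU co-primary endpoint. The same imputed values feed other ranked endpoints in SAP 3.2: PRO remission at Week 4 and corticosteroid-free PRO remission (EU), and PRO remission at Week 12 (first-ranked for the US). SAP 9.2 says the aim is a reliable estimate of the treatment effect as it would have been without the pandemic. Dropping the link between the endpoint's two components works against that aim, even if only slightly.

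**Working it through.** **1. The plan's own figure.** SAP 2.4 states: "Assuming a rate of 12% for clinical remission per PROs in the placebo group and 29% in the upadacitinib group at Week 12", with 330 and 165 subjects, Fisher's exact test, two-sided 0.05 and at least 95% power. Recomputed power is 99.4% (exact Fisher) or 99.5% (normal approximation), so the stated floor is met.

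**2. Inputs.** From the SAP: remission of 29% and 12%, a difference of 17.0 points. Assumed, because the documents give none of them: residual SF-AP correlation ρ of 0.3 to 0.7, within-symptom correlation of 0.7 between adjacent visits, and a COVID-missing share f of 1% to 10%.

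**3. Correlation wholly lost.** Treat SF and AP as bivariate normal with equal margins m. Choose m so that P(both low) equals the planned rate p. Separate imputation then gives m × m in place of p. For example, at ρ = 0.5 on upadacitinib, m = 0.456 and m² = 0.208, against p = 0.29.

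**4. Own history used.** Now let each Week 12 value be imputed from that symptom's own values through Week 8. Each history carries part of the shared signal, so less is lost.

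Remission among imputed subjects (joint imputation gives 29% and 12%):

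| ρ | Wholly lost, upadacitinib / placebo | Own history to Week 8, upadacitinib / placebo |
|---|---|---|
| 0.3 | 24.2% / 8.3% | 26.5% / 10.1% |
| 0.5 | 20.8% / 6.2% | 24.7% / 8.9% |
| 0.7 | 17.1% / 4.4% | 22.4% / 7.6% |

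At ρ = 0 there is no bias. At ρ = -0.2 the sign reverses (32.1% / 14.9%).

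**5. Effect on the trial.** The treatment difference shrinks by f × [(29 - imputed upadacitinib %) - (12 - imputed placebo %)]. With f = 5% and the correlation wholly lost:
- ρ = 0.3: 0.05 × (4.8 - 3.7) = about 0.06 points
- ρ = 0.7: 0.05 × (11.9 - 7.6) = about 0.22 points

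The difference therefore moves from 17.0 to between 16.94 and 16.78 points. In subjects, this is 0.8 to 2.0 upadacitinib responders and 0.3 to 0.6 placebo responders. At f = 2% the difference is 16.98 to 16.91, and at f = 10% it is 16.88 to 16.57. Power changes by less than 0.1 percentage point throughout.

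**6. Comparison with a planned sensitivity analysis.** NRI-NC sets every COVID-missing subject to non-response. At f = 5% that gives 0.95 × 17.0 = 16.2 points, a larger reduction than separate imputation causes.

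**The case against.** **The SAP never says the runs are separate.** This is correct. The sentence on PROC MI does not address it, a seed table is not a predictor list, and a run with its own seed could still include the other symptom. A reader might infer that the plan definitely excludes SF from the AP model. The text supports only that this is the natural reading.

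**The direction is not established.** A reader might also infer that imputed remission is certain to be too low. That needs a positive residual correlation after conditioning on treatment, strata, demographics and each symptom's history. Both symptoms score in the same direction in the CDAI, so a positive value is plausible, but the documents report none.

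**The wholly-lost figures are an extreme case.** This also stands. Own history to Week 8 removes about half of the upadacitinib loss in the cases shown. Unequal margins reduce it too: at ρ = 0.7 with one symptom twice as likely to qualify as the other, the 17.1% becomes 19.8%. The larger fall on upadacitinib holds in percentage points only. In relative terms placebo falls more (at ρ = 0.5, 48% against 28%).

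**Few subjects may be affected.** Only COVID-related gaps are imputed. SF and AP come from a diary that "will be collected electronically via a handheld device into which the subject will record the required pieces of information on a daily basis", and SAP Appendix D needs only four usable days within 14. However, that appendix ties the calculation to a visit with CDAI components, so a missed visit could still leave both values missing. The 5% share is an illustration.

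**Planned analyses already bound the effect.** NRI-NC is more extreme, and the tipping-point analysis (SAP 9.2.3) assigns binary response directly, so it does not depend on how SF and AP are imputed. Both show how far the result could move, but neither corrects the main estimate.

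**Conclusion.** The point holds as a minor improvement to the primary imputation method. The SAP most naturally reads as imputing SF and AP separately for an endpoint that requires both. Any positive residual correlation would then make imputed PRO remission too low in both arms among COVID-missing subjects.

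Over assumed correlations of 0.3 to 0.7, imputed remission would be 24% to 17% in place of 29% and 8% to 4% in place of 12% if the correlation is wholly lost. With own history to Week 8 (within-symptom correlation 0.7 assumed) it would be about 26% to 22% and 10% to 8%. At an assumed 5% COVID-missing, the difference is diluted by at most about 0.05 to 0.2 points.

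A reader might infer that the EU co-primary result is at risk. The calculation does not support that: in the cases with positive correlation the shift is towards no difference, power is essentially unchanged, and the planned NRI-NC analysis is harsher. The US co-primary endpoints do not use this imputation, because CDAI and SES-CD have their own rows in Table I-1.

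**What to change.** In SAP 9.2.1, state that SF and AP at all visits are imputed in one joint model, and that PRO remission is derived within each completed dataset. An acceptable alternative is to include each symptom's values as predictors of the other. Make Table I-1 match: one merged SF/AP row with one seed pair under the joint model, or a note on the added predictors under the alternative. If joint imputation was already intended, the same edit makes that explicit.

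The cost is one or two sentences, a table edit and one merged procedure call. No new data are needed, and the planned sensitivity analyses stay as they are.
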